2.2 Stage A2

The aim is to find the M6620 (Berzosertib) treatment schedule when combined with palliative combination chemotherapy (Cisplatin and Capecitabine) that is associated with no more than a 30% dose limiting toxicity rate. Four treatment schedules are proposed. Each schedule comprises a specific combination of dose and dosing frequency. There are two possible M6620 (Berzosertib) doses and two dosing frequencies (see section 8.2). Chemotherapy dose remains consistent across all treatment schedules.

The treatment involves six cycles of chemotherapy with three weekly Cisplatin and Capecitabine and M6620 (Berzosertib) at a pre-determined frequency dependent on the treatment schedule allocated to the individual patient. The follow-up of a further 8 weeks provides a total observation window of 26 weeks. DLT assessments will be carried out during the first 4 weeks of treatment. The MTD will be determined during this period using the TiTE-CRM. An initial cohort of three patients will receive the starting schedule (lowest dosing frequency) at the starting dose. The fourth patient will not be recruited until all three patients have been followed for a minimum of 4 weeks from the start of chemotherapy or until the occurrence of a DLT.

From the fourth patient, all eligible patients will be continuously recruited and the TiTE-CRM will be used to assign their treatment schedule. To ensure enough information is accumulated to inform the assignment of the treatment schedule to the subsequent patient, recruitment will be managed by allocating treatment slots (see section 4.4 for further details).

2.2.1. Stage A2 stopping rules

Stage A2 will stop for safety if, at any point in the trial, there is sufficient evidence to suggest that schedule 1 is too toxic. More specifically, we will consider schedule 1 to be too toxic if, given all the available data, there is a high probability that the DLT rate is greater than the target toxicity level of 0.3. If the first three patients recruited to Stage A2 have DLTs at treatment schedule 1, then the starting schedule (treatment schedule 1) will be deemed too toxic and the trial will stop.

The trial will stop for success when either six patients have been assigned to the fourth treatment schedule (140 mg/m² of M6620 (Berzosertib) twice weekly) or 20 patients in total have been recruited, whichever occurs first. When six patients in Stage A2 have been assigned to the fourth treatment schedule, recruitment to Stage A2 will be paused until there is full DLT follow-up information on at least five patients. If the MTD has changed, recruitment to Stage A2 may start again.

Based on simulations and assuming a patient will be recruited every 3 weeks, the average number of patients required for Stage A2 is 16, which we aim to recruit in 12 months.

2.3 Stage B

The aim is to find the M6620 (Berzosertib) treatment schedule when combined with chemoradiotherapy that is associated with no more than 45% dose limiting toxicity rate on the basis that conventional oesophageal chemoradiation causes a grade 3 and 4 toxic event rate of 28% haematological toxicity and 63% non-haematological toxicity, of which 34% is gastrointestinal, as reported in the standard arm of the SCOPE1 study. Comparable toxicity rates were described in the standard arm of the PRODIGE5/ACCORD17 study: grade 3 and 4 neutropenia 29% and grade 3 and 4 dysphagia and oesophagitis 33% (13). A maximum of 25 patients will be recruited to Stage B.

There are three proposed M6620 (Berzosertib) treatment schedules (same dose but increasing dosing frequencies) to be explored during Stage B. Before each patient enters Stage B, a TMG will be held to confirm recruitment. If permitted to enrol in the study, the patient will also be assigned a provisional treatment schedule based on the TiTE-CRM's recommendation. If necessary, a confirmation meeting for the M6620 (Berzosertib) treatment schedule assignment will occur prior to the start of chemoradiotherapy 6 weeks after a patient is recruited. This will maximise the accumulation of information on each patient before deciding on the treatment schedule for the subsequent patient.

The dose of M6620 (Berzosertib) in Stage B will be 140mg/m², allocation will start on schedule 1, which is the middle of the 3 schedules. Recruitment will be continuous; however, escalation will not occur until at least one patient full DLT window of 24 weeks is complete. At this point escalation to schedule 2 will be possible if it is estimated to be safe, and dose decisions thereafter will be made once each new patient is recruited and confirmed (if there is reason to think their allocation may have changed) when they have been treated for 6 weeks (the induction period which is the same for all schedules). De-escalation to schedule -1 is possible at any point in the trial. Although recruitment will be continuous, the TMG retain the option to pause recruitment should they decide more follow-up data is needed before continuing. This may be, for example, to prevent too many patients being treated with a sub-optimal, or too toxic, schedule. No more than 7 patients will be treated on schedule 1 before there is full follow-up data on at least one patient.

We will recommend starting stage B:

- If 10 patients have been recruited to A1 and it has not restarted at the lower dose
- If 10 patients have been assigned to at least schedule 3 in A2 (i.e. are on any of the schedules with a dose of 140mg/m²) or the stopping rule is satisfied (6 treated on schedule 4)

If one of the above starting rules are satisfied then an SRC meeting will be convened to review the data and may recommend starting stage B.

2.3.1 Stage B stopping rules

Stage B will stop for safety if, at any point in the trial, there is sufficient evidence to suggest that schedule -1 is too toxic. More specifically, we will consider schedule -1 to be too toxic if, given all the available data, there is a high probability that the DLT rate is greater than the target toxicity level of 0.45. There will be no early stopping rules for success. We expect to recruit a minimum of 15 patients.

2.4 Duration of patient participation

Stage A1: Participants will be in the study for 12 weeks from first trial dose or intervention to last protocol visit.

[figure not shown]
Stage A2: Participants will be in the study for maximum of 26 weeks from first trial dose to last protocol visit.

Stage B: Participants will be in the study for 24 weeks from first trial dose or intervention to last protocol visit.

2.5 Post-trial care and follow-up

Following the end of study visit, patients will receive standard care. They may receive further chemotherapy if appropriate as per the standard practice of the clinical care team. Patients in Stage A1 & A2 will be followed for progression free survival, overall survival and late toxicity via routine medical oncology follow up clinics. The physician will be asked to provide these data at 6 and 12 months from the start of treatment for Stage A1 and Stage A2.

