14.4.1 Expected adverse events associated with Radiotherapy

Fatigue, oesophagitis, odynophagia, dyspnoea, nausea, vomiting, skin erythema and desquamation. Late toxicity risks of lung fibrosis, oesophageal stricture, oesophageal perforation, cardiac toxicity and secondary malignancy.

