14.9 Reporting Adverse Events on the CRF

All AEs, including Serious AEs must be recorded on the case report forms (CRF) for that patient (unless otherwise specified in section 14.10). The information provided will include date of onset, event diagnosis (if known) or sign/symptom, severity, time course, duration and outcome and relationship of the AE to study drug. Any concomitant medications or any other therapy used to treat the event must be listed. The Investigator will provide an “other” cause for serious AEs considered to be unrelated to the study drug. Sites should ensure data entered into the CRF is consistent with the SAE report information where applicable.

Each separate AE episode must be recorded. For example, if an AE resolves completely or resolves to baseline and then recurs or worsens again, this must be recorded as a separate AE. For AEs to be considered intermittent, the events must be of similar nature and severity.

AEs occurring from the first dose of study medication up to the end of study visit must be recorded on the CRF. AEs may be spontaneously reported by the patient and/or in response to an open question from study personnel or revealed by observation, physical examination, or other diagnostic procedures. Any clinically relevant deterioration in laboratory assessments or other clinical finding is considered an AE. AEs which result in early withdrawal must be reported using the Early Withdrawal Form.

Terms and Grading of Events

All adverse events and toxicities must be graded according to the NCI Common Terminology Criteria for adverse events (NCI-CTCAE) Version 4.0 (currently up to Version 4.03).

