20.4 Clinical study report

All clinical data will be presented at the end of the study as data listings. These will be checked to confirm the lists accurately represents the data collected during the course of the study. The trial data will then be locked and a final data listing produced. The locked trial data may then be used for analysis and publication. The Clinical Study Report will be based on the final data listings. The Clinical Study Report will include the analysis of the routine survival data collected up to 12 months for Stage A1 and A2. The CSR will be presented within 1 year of end of trial.

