2.2 Objectives

Stage A1		
Primary Objective	Endpoints/ Outcome Measures	Time point(s) for evaluation of end point

 To determine the best tolerated M6620 treatment schedule (or phase II recommended dose (RPTD)) administered concomitantly with Radiotherapy only in the palliative treatment of oesophageal cancer 	Highest treatment schedule resulting in less than 25% dose limiting toxicity (DLT) rate (see section 9.1.2 for DLT definitions)	
 Week 9
Secondary Objectives	Endpoints/ Outcome Measures	

 To determine the safety and toxicity profile of M6620 administered concomitantly with RT only in the palliative treatment of oesophageal cancer 	
 Any toxicity grade ≥ 3 graded according to CTCAE v4.03 and length of time for toxicity to resolve 	
 During radiotherapy Weeks 1-3 Week 4, 9 and week 12

 To determine if M6620 can be delivered in combination with palliative RT 	
 Proportion of patients completing at least 75%, 90% and 100% of the planned RT dose 	
 End of radiotherapy End of Week 3

 Efficacy of the combination 	
 Objective tumour response (OR) as evaluated by CT scan and quantified by Response Criteria Evaluation (RECIST 1.1) PFS and OS from D1 In field radiotherapy control 	
 12 weeks 6 and 12 months
Stage A2		
Primary Objective	Endpoints/ Outcome Measures	Time point(s) for evaluation of end point

 To determine the best tolerated M6620 treatment schedule (or phase II recommended dose (RPTD)) administered concomitantly with chemotherapy (Cisplatin and Capecitabine) only in the palliative treatment of solid cancer 	
 Highest treatment schedule resulting in less than 30% dose limiting toxicity (DLT) rate (see section 9.1.2 for DLT definitions) 	
 Week 4
Secondary Objectives	Endpoints/ Outcome Measures	

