7.2.2 Secondary Outcomes

Safety and Toxicity Profile of the M6620 (All Stages)

The number (proportion) of patients who have had an AE recorded should be reported by schedule group. The number (proportion) of patients who have experienced one, two, three or more AEs will also be provided by schedule group. It is intended that the number of AEs recorded, the number of AEs per grade and the outcome will be reported.

This analysis will be repeated twice: once using serious adverse events (SAEs) and once using serious adverse reactions (SARs). Note: SARs are SAEs that are recorded as being possibly, probably or definitely related to a component of treatment. For SARs, the treatment component the event was related to may also be described.

Details of any SUSARs will be reported in the statistical report; the schedule group for the affected patient will be indicated.

Dose limiting toxicities are classed as SAEs in CHARIOT and will be analysed as described above. Length of time for toxicities to resolve will also be summarised and presented as mean (SD) or median (IQR).

Proportion of patients completing planned dose (All Stages)

To determine the ability to deliver the M6620 with palliative radiotherapy (Stage A1) and palliative chemotherapy (Stage A2), the proportion of patients completing at least 75%, 90% and 100% of the planned dose will be tabulated by schedule group.

A phase I dose escalation safety study combining the ATR inhibitor VX-970 with chemoradiotherapy in oesophageal cancer using time to event continual reassessment method (funded by CRUK and Merck)
EudraCT Number: 2015-003965-27

To determine tolerance and ability to deliver M6620 in combination with standard definitive chemoradiotherapy in Stage B, the proportion of patients completing at least 80% of the planned chemotherapy dose and at least 20 fractions of radiotherapy will be tabulated by schedule group.

Efficacy of the combination (All Stages)

Objective tumour response will be classified according to the RECIST v1.1 criteria. The number and proportion of patients who achieve Complete Response (CR), Partial Response (PR), (Stable Disease) SD and Progressive Disease (PD) will be reported overall and by treatment schedule.

Overall survival (OS) will be presented by stage using Kaplan Meier graphs along with two-sided 95% confidence intervals. Median and quartile OS will also be presented together with their 2-sided 95% confidence intervals if applicable.

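### Stage A1 promises late toxicity at 6 and 12 months, but no graded item, endpoint time point or named analysis carries it past week 12

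*Protocol*

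**What the plan says.** Protocol 2.5 states: "Patients in Stage A1 & A2 will be followed for progression free survival, overall survival and late toxicity", through routine clinics. It then says "The physician will be asked to provide these data at 6 and 12 months from the start of treatment", for both A1 and A2. Protocol 14.4.1 names the harms expected from radiotherapy in the long run: "Late toxicity risks of lung fibrosis, oesophageal stricture, oesophageal perforation, cardiac toxicity and secondary malignancy". Protocol 14.5 treats toxicity as late when it begins 6 weeks after radiotherapy ends. It sends late grade 2 events to the AE CRF, and late grade 3 or worse events to both the AE CRF and the expedited form, with no end date.

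Other sections stop sooner or ask for less:

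- **Endpoint.** The A1 toxicity time points in SAP 2.2 are "During radiotherapy Weeks 1-3 Week 4, 9 and week 12". Protocol 3.1.1 agrees.
- **Recording.** Protocol 14.9: "AEs occurring from the first dose of study medication up to the end of study visit must be recorded on the CRF". For A1 the last protocol visit is at week 12 (2.4).
- **6- and 12-month request.** Protocol 5.4.3 asks about death, progression, further intervention and events of clinical significance. It has no toxicity grade, no onset date and no late-toxicity item. Section 5.4.6 (A2) is similar.
- **Analysis.** SAP 7.2.2 says "The number (proportion) of patients who have had an AE recorded should be reported by schedule group" and repeats this for SAEs and SARs. It does not name late toxicity.
- **Report.** Protocol 20.4: "The Clinical Study Report will include the analysis of the routine survival data collected up to 12 months for Stage A1 and A2". Late toxicity is not mentioned beside survival.

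**The concern.** Section 2.5 names three outcomes in one sentence. PFS and OS each have time points beyond week 12 in the objectives tables and a Kaplan-Meier analysis in SAP 7.2.2. Late toxicity has neither.

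This matters most in A1, where M6620 is combined with radiotherapy for the first time (Protocol 1.4). A secondary objective of that stage is the safety and toxicity profile of the combination. If a drug is given to enhance radiation effect, late normal-tissue injury is a harm that readers will look for. If the stated recording and endpoint rules are followed, the tabulated A1 profile ends soon after the late period begins, although the sites are still being asked for information at 6 and 12 months.

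**Working it through.** **1. The plan's own figures.** A1 has 3 weeks of radiotherapy (Protocol 2.1). DLT window: 3 + 6 = 9 weeks, as stated. Last visit: 3 + 9 weeks after radiotherapy (5.4.3) = week 12, as stated in 2.4.

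**2. Start of the late period in A1.** With the 6-week threshold of 14.5: 3 + 6 = week 9. In days, the last fraction is on day 19, late onset starts at 19 + 42 = day 61, and the last visit falls at 19 + 63 = day 82. The difference is 21 days, or 3 weeks.

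**3. Share of the late period that routine reporting covers.**

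- To month 12: 52 − 9 = 43 weeks, of which 12 − 9 = 3 are covered. 3/43 = 7%, leaving 40 weeks.
- To month 6: 26 − 9 = 17 weeks. 3/17 = 18%, leaving 14 weeks.

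**4. Does SAE reporting fill the gap?** Protocol 14.7 runs general SAE reporting to the later of 30 days after the last dose and the end of the DLT period. On schedule, A1 treatment ends by day 19, so the first limit is 19 + 30 = day 49 (week 7) and the second is week 9. General SAE reporting therefore ends as the late period opens. After that, 14.7 captures SAEs that the investigator relates to a study drug. Events put down to radiotherapy alone, and non-serious events, are outside that route.

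**5. Stage A2.** There is no radiotherapy. Treatment of 18 weeks plus 8 gives week 26, which is also the last toxicity time point. Six months is 365.25/2/7 = 26.1 weeks. For a patient who completes six cycles, the 6-month report coincides with week 26, so only the 12-month report lacks a time point.

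**6. How many A1 patients could contribute.** Protocol 1.1 quotes a median survival of 203 days with radiotherapy alone. Assuming exponential survival, S(t) = 2^(−t/203):

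- S(182) = 0.537; S(365) = 0.288.
- With the expected 18 patients (Protocol 17.1): 9.7 alive at 6 months and 5.2 at 12 months.
- Over the simulated range of 10 to 20 patients: 5.4 to 10.7 at 6 months and 2.9 to 5.8 at 12 months.

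These few survivors may be spread over up to six schedules.

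**The case against.** The strongest reply is that late harm has other routes into the report.

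- Protocol 20.4 presents all clinical data as listings and bases the study report on them.
- Protocol 18.1 tabulates treatment-related toxicity by type and grade, and SAP 7.2.2 tabulates AEs, SAEs and SARs. Neither sets an end date.
- Protocol 14.5 lists late grade 2 and grade 3 or worse events without a time limit.
- Drug-related SAEs are reportable at any time, and SAP 7.2.2 counts possibly related SAEs as SARs.
- Stage B also combines M6620 with radiotherapy. It defines late DLTs and follows patients to week 24, which is 24 − (11 + 6) = 7 weeks into its own late period.

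Much of this stands, and it rules out several readings that a reader might infer:

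- That late harm is reported only for 3 weeks. The routes above contradict that. The 3 weeks are also weeks 9 to 12 of A1, not the first 3 weeks of treatment.
- That A2 has the same gap. It does not, as step 5 shows.
- That graded 12-month data are already in hand. The request in 5.4.3 is ungraded and undated, so worst RTOG grade or competing-risk incidence by schedule could not be built from it. With about five survivors at 12 months, incidence by schedule would say little anyway.

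The reply does not remove the gap. Tables without an end date can still hold only what is recorded, and 14.9 closes recording at week 12 while 14.5 leaves it open. The documents do not say which governs. A listing of ungraded events is not a planned summary. Reliance on drug attribution is weak when the question is whether the drug worsens radiation injury.

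**Conclusion.** The point holds for Stage A1 in limited form. Late toxicity is promised at 6 and 12 months but has no graded collection item, endpoint time point or named analysis. Apart from drug-related SAEs and data listings, the reported safety profile reaches 3 of the 43 weeks of the late period to month 12. The likely loss is non-serious late toxicity and events attributed to radiotherapy alone after week 12. In A2 the gap is the 12-month report only.

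The 3-in-43 figure rests on the 6-week late-onset threshold of 14.5 and on 14.9 governing AE recording. If the open-ended rows of 14.5 govern instead, more would be recorded, though still without a named late-toxicity analysis. The survivor counts rest on an external median and an exponential curve, and serve only to show how sparse the data would be. DLT assessment, schedule allocation and stopping rules are unaffected. This is an inexpensive improvement that would complete the trial's own safety objective.

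**What to change.** 1. Reconcile Protocol 2.5, 5.4.3, 5.4.6, 14.5 and 14.9 on how long late toxicity is recorded.
2. Add a toxicity grade and onset date to the existing 6- and 12-month request.
3. Extend the A1 toxicity time points in Protocol 3.1.1 and SAP 2.2 to 6 and 12 months.
4. Add to SAP 7.2.2, and name in Protocol 20.4, one descriptive table or listing of late grade 3 or worse events by assigned schedule. Show the number alive and assessed at each time, and deaths without late toxicity, so that a low count is not mistaken for low risk. If cumulative incidence is shown, pool it over schedules and treat death as a competing event.

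The cost is protocol and SAP wording, a small addition to the follow-up form, and one table or listing. The estimates will be imprecise, because few A1 patients are likely to be alive at 12 months and grading would come from routine clinics. No dose or treatment rule changes.

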2.6 Recruitment Schematic

3 OBJECTIVES AND ENDPOINTS

3.1 Stage A

3.1.1 Stage A1

Primary Objective	Endpoints/ Outcome Measures	Time point(s) for evaluation of end point

 To determine the best tolerated M6620 (Berzosertib) treatment schedule (or phase II recommended dose (RPTD)) administered concomitantly with Radiotherapy only in the palliative treatment of oesophageal cancer 	Highest treatment schedule resulting in less than 25% dose limiting toxicity (DLT) rate (see section 9.1.2 for DLT definitions)	
 Week 9
Secondary Objectives	Endpoints/ Outcome Measures	

 To determine the safety and toxicity profile of M6620 (Berzosertib) administered concomitantly with RT only in the palliative treatment of oesophageal cancer 	
 Any toxicity grade ≥ 3 graded according to CTCAE v4.03 and length of time for toxicity to resolve 	
 During radiotherapy Weeks 1-3 Week 4, 9 and week 12

 To determine if M6620 (Berzosertib) can be delivered in combination with palliative RT 	
 Proportion of patients completing at least 75%, 90% and 100% of the planned RT dose 	
 End of radiotherapy End of Week 3

 Efficacy of the combination 	
 Objective tumour response (OR) as evaluated by CT scan and quantified by Response Criteria Evaluation (RECIST 1.1) PFS and OS from D1 In field radiotherapy control 	
 12 weeks 6 and 12 months
Tertiary Objectives	Endpoints/ Outcome Measures	

 Explore tumour characteristics associated with response 	
 Genotyping of tumours 	
 Pre-trial archival biopsy

3.1.2 Stage A2

Primary Objective	Endpoints/ Outcome Measures	Time point(s) for evaluation of end point

 To determine the best tolerated M6620 (Berzosertib) treatment schedule (or phase II recommended dose (RPTD)) administered concomitantly with chemotherapy (Cisplatin and Capecitabine) only in the palliative treatment of solid cancer 	
 Highest treatment schedule resulting in less than 30% dose limiting toxicity (DLT) rate (see section 9.1.2 for DLT definitions) 	
 Week 4
Secondary Objectives	Endpoints/ Outcome Measures	

 To determine the safety and toxicity profile of M6620 (Berzosertib) administered concomitantly with 	
 Any toxicity grade ≥ 3 graded according to CTCAE v4.03 and 	
 During chemotherapy Week 1-18

chemotherapy (Cisplatin and Capecitabine) only in the palliative treatment of solid cancer	length of time for toxicity to resolve	
 • Week 20, 26
• To determine if M6620 (Berzosertib) can be delivered in combination with palliative chemotherapy	
 • Proportion of patients completing at least 75%, 90% and 100% of the planned dose 	
 • End of chemotherapy Week 18
• Efficacy of the combination	
 • Objective tumour response (OR) as evaluated by CT scan and quantified by Response Criteria Evaluation (RECIST 1.1) • PFS and OS from D1 	
 • Week 6, 12, 18, 26 • Week 26 & 12 months

